**Vernakalant IV Sterile Concentrate Prospective Safety Registry Study**

Sponsor Protocol Identifier: 6621-049-00

3 August 2016

Day 1 Start date of vernakalant IV administration	From start of first infusion through the 24- hour period following last infusion of vernakalant IV or until discharge/end of medical encounter (whichever occurs earlier)	24 hours
---	--	----------

## **Vernakalant IV Sterile Concentrate Prospective Safety Registry Study**

Sponsor Protocol Identifier: 6621-049-00

3 August 2016

---

### **5.2 Duration of Study**

The study is anticipated to be launched by Q3 2011. The study is expected to take approximately 6-7 years to complete, dependent on the timing of vernakalant IV commercial availability in each country, local EU member regulatory approval of the PASS, and the rate of market uptake of vernakalant IV. Site recruitment for the study will begin in third-quarter 2010 and will continue through study launch or as needed. Interim reports will be provided with each periodic safety update report (PSUR/PBRER) for Vernakalant Sterile concentrate (BrinavessTM) and submitted to CHMP after the study is launched. Assuming an estimated 74 months of active enrolment into the study, the final PASS report would be targeted for submission to CHMP by Q1 2018.

### **5.3 Study Population**

The study population will include patients) who are treated with vernakalant IV in acute care and inpatient hospital settings. The decision to treat with vernakalant IV will be made by the treating physician independently of this study. The epidemiology of atrial fibrillation suggests that prospective patients are more likely to be elderly, and somewhat more likely to be male than female. At each site, consecutive patients will be enrolled into the PASS, to the extent possible.

### **5.4 Number of Patients**

The study will enrol a total of 2,000 patients across participating EU member and other European countries, subject to adequate uptake and use of vernakalant IV within the 6-7 year study period to provide timely data regarding product safety. Based on the results of a pilot-test of procedures completed by the Sponsor in preparation for this study, it is recognized that enrolment of patients in hospital and urgent care setting may be challenging based not only on the estimated product uptake during the planned data collection period but also on the variability in clinical practice use of electrical versus pharmacological cardioversion in many European countries. If during the study it becomes apparent that the target patient number may not be met within the specified enrolment period, the Sponsor will initiate discussions with the CHMP in a timely fashion to ensure sample size is sufficient to provide reasonable statistical precision for the associated 95% confidence intervals for each HOI, as discussed in Section 10.7. A sufficient number of sites to meet enrolment requirements will be recruited to participate in the PASS.

## **6 SELECTION OF PATIENTS**

### **6.1 Inclusion Criteria**

The inclusion criteria for enrolment are:

- Patients treated with vernakalant IV, independently of this study

## **Vernakalant IV Sterile Concentrate Prospective Safety Registry Study**

Sponsor Protocol Identifier: 6621-049-00

3 August 2016

---

- Subjects and/or legal guardians willing to provide informed consent and/or informed assent according to local regulations

### **6.2 Exclusion Criteria**

The exclusion criteria for enrolment are:

- Enrolment in an investigational drug or device clinical trial in the 30 days prior to study enrolment. Participation in another non-interventional drug or device study or registry is permitted.

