## 7.2 Collection of Data Retrospectively

To minimize further delay to completion of the study, data will be collected retrospectively from patients who have received Brinavess™ but were not enrolled in the study. To reflect today's real world setting, retrospective data will only be collected from patients who received Brinavess™ after the additional risk minimization measures were implemented in April 2013. This would mean that data from patients would be included both retrospectively and prospectively at all new and existing sites.

The inclusion of these retrospective data from patients already treated with Brinavess™ would allow the primary objective study to be met fully, whilst facilitating the timely completion of this trial.

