**Vernakalant IV Sterile Concentrate Prospective Safety Registry Study**

Sponsor Protocol Identifier: 6621-049-00

3 August 2016

---

At the completion of the study, stratified analyses will be used to present the results. Full statistical methods and analyses will be described in the Statistical Analysis Plan (SAP).

Patients are consecutively enrolled into SPECTRUM based on when they present at the participating site. In order to minimize any potential selection bias at the patient level, retrospective data collection will be conducted to include all patients already treated with BrinavessTM but not enrolled in SPECTRUM, at existing and newly qualified sites, with available key data. Specifically, data will be included from all patients who;

1. Have received BrinavessTM since April 2013 but were not enrolled in SPECTRUM.
2. Have available in their hospital records the key data variables as stipulated in section 7.2.1.
3. Provide their informed consent or the site obtains a waiver from their IEC.

Both retrospectively and prospectively included patients have to fulfill the same inclusion and exclusion criteria. As neither group of patients are selected randomly, this approach is not expected to yield selection bias. In addition, results will be reported overall and stratified by method of enrollment. As those who refuse to consent to participate, will not have provided their consent to use their data it would not be possible to compare baseline characteristics of those who refuse vs those who participate. To ensure the overall sample is not dominated by any one site or country by the inclusion of retrospective data, any site or country who reaches their limit based on the inclusion of retrospective data will be closed and the resources used to open other sites/countries. Enrolment will be capped at 10% per site (200 patients) and 40% per country (800 patients). This cap includes collection of patient data both prospectively and retrospectively.

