### **Informed consent**

Patients who fulfil the criteria above will be contacted either at clinic during their next routine follow up cardiology appointment, or by phone and / or mail. The approved informed consent form will then be discussed in detail with the patient and if they agree to take part, the patient will personally sign and date the consent form.

If local regulations permit, sites may also ask their IEC for an informed consent waiver.

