### **Identification of retrospective patients**

As soon as local regulatory and Ethics Committee approval are obtained (where applicable) sites will be able to enrol retrospective patients concurrently with prospective patients.

Strategies for identifying retrospective patients will vary between sites as a result of varying staff availability and record keeping. Sites with searchable electronic patient records for example will find it easier to identify patients than sites without.

Several methods will be employed to identify retrospective patients who have been treated with Brinavess since April 2013.

1. Patients will be approached at their routine clinic visit. If a study team member notices during this visit that Brinavess treatment has been previously given, the study will be discussed with the patient at this time and asked if they are willing to give their consent to take part.
2. Following a search of the hospital records,
  - a. Identified patients will receive a telephone call, the study discussed with them and at their next routine visit asked if they are willing to give their consent to take part. OR
  - b. Identified patients will receive a telephone call, the study discussed with them, information mailed to the patient and then the patient will be asked to sign and mail back the completed consent form. OR

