3.4 Derived Variable Definitions

The following derived/calculated values will be used:

- Age at enrolment = [(date of informed consent – date of birth) + 1]/365.25, or self-reported age if date of birth is not available.
- BMI = Weight (Kg)/Height (m)². English standard units should be converted to international or metric units.
- (S)AE or HOI onset in days and time (in hours or minutes) following vernakalant IV infusion = date/time of onset or (S)AE-date – date/time of start of first infusion.
- Duration or period = (stop time – start time). Note there are key durations that include, but are not limited to, duration of vernakalant IV infusions and duration of HOI and SAE.
- Vernakalant IV dose per body weight = vernakalant IV dose (mg) / body weight (kg).
- Duration of time to conversion to sinus rhythm = (date/time of conversion to sinus rhythm – date/time of start of first infusion).
- Percentage of weight-based dosing recommendation per label (%) = (Vernakalant IV dose [mg/kg] / Recommended vernakalant IV dose [mg/kg]) * 100. Range from 0% to above 100%, with 100% indicating that dose is equal to recommended dose, calculated per first or second infusion. Patients with cumulative doses greater than the maximum recommended dose will be noted (overall and for first and second infusion, separately).
- Duration of current AF in hours = (Vernakalant administration date/time - AF onset date/time).

- Time since first AF diagnosis = (Start date of Vernakalant IV administration - Date of first AF diagnosis).
- Rate of conversion to sinus rhythm for at least one minute within 90 minutes of start of first vernakalant IV administration = (Number of relevant patients converted to sinus rhythm for at least one minute within 90 minutes of start of first vernakalant IV administration) / (Total number of relevant patients administered vernakalant IV). Rate of conversion can be evaluated based on different types of patients, e.g. all patients receiving vernakalant IV or all such patients with other restrictions.
- Elevated liver enzymes (inclusive of possible abnormal liver function or liver injury) = an increase above upper limit of normal (ULN) for alanine aminotransferase (ALT), aspartate aminotransferase (AST), or total bilirubin (TB) or conjugated bilirubin. [1,2]
- Total hospital length of stay (hours) = (Date/time of discharge or release of facility – Date/time of hospital admission).

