- Modification of Diet and Renal Disease (MDRD) estimated Glomerular Filtration Rate (GFR) (mL/min per 1.73 m²) = $186 \times (\text{Serum creatinine } [\text{Scr}])^{-1.154} \times (\text{Age})^{-0.203} \times (0.742 \text{ if female}) \times (1.210 \text{ if Black})$. [2]
- Time between Current and Previous Study Enrolment = (Informed consent date of current enrolment – Informed consent date of previous study enrolment).

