5.1 Patient Disposition, Enrolment, and Demographics

5.1.1 Patient Disposition

NOTE: Patients may be enrolled in the study more than once in association with multiple treatment episodes of vernakalant IV. The study protocol does not prohibit multiple enrolments for a single patient. Patients receive a new, unique study ID at each new vernakalant treatment episode. **Note: the vernakalant treatment episode as referenced does not pertain to each infusion of vernakalant, as one treatment episode may involve multiple vernakalant infusions.** A summary of patients with multiple treatment episodes included in the analysis population set and the number of previous treatment episodes, if any, will be provided in the patient disposition table. All study tables and listings will treat each patient's subsequent administrations of vernakalant IV as occurring independently. For each patient with multiple treatment episodes, information regarding each episode including dates of informed consent, will be listed (**Listing 6**). Each patient's cumulative profile of SAEs (including HOIs) and contraindications by treatment episode will also be listed (**Listings 7-8**).

Patient disposition, per administration of vernakalant IV, will be summarised, as follows (**Table 2, Figure 1**):

- Total number of patients screened from site enrolment log (**Figure 1** only) and reasons for non-participation listed below, if available
 - No Informed Consent (Patient/Guardian unable to and/or refusal to give consent)
 - Patient not approached prior to vernakalant administration
 - Patient enrolled in an investigational drug or device clinical trial in the past 30 days prior to vernakalant administration
- Total number of patients enrolled in the registry
 - Total number of patients discontinued from the study due to conversion to sinus rhythm before vernakalant administration
- Total number of patients in the analysis population. All enrolled patients who meet the eligibility criteria and sign the informed consent form and are administered vernakalant IV are included in the analysis population. Patients discontinued from the study due to conversion to sinus rhythm before vernakalant administration or, based on patient request or ethic committee requirements, withdrawal of patient consent, will not be included in the analysis set.

- Total number of patients with single and multiple vernakalant treatment episodes in the analysis population

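### The 30-day investigational-trial exclusion is counted back from study enrolment, so for retrospective patients who consent 30 or more days after treatment it tests none of the pre-infusion period, and it does not match the SAP's description

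*Protocol*

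**What the plan says.** Protocol 6.2 has one exclusion criterion: "Enrolment in an investigational drug or device clinical trial in the 30 days prior to study enrolment". The synopsis repeats it. So does the annex for German sites, which also adds contraindications.

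Protocol 7.2 opens the study to patients already treated: "retrospective data will only be collected from patients who received Brinavess™ after the additional risk minimization measures were implemented in April 2013". Their consent comes later. They "will be contacted either at clinic during their next routine follow up cardiology appointment", or by phone or mail, and a site may instead seek a consent waiver from its ethics committee. No separate eligibility rule is given for them: "Both retrospectively and prospectively included patients have to fulfill the same inclusion and exclusion criteria". Section 7.2 relies on these shared criteria when it argues that adding retrospective patients should not cause selection bias.

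The protocol does not define the date of enrolment. SAP 3.4 uses the consent date, for example "Age at enrolment = [(date of informed consent – date of birth) + 1]/365.25", and it also measures the time between successive enrolments from consent dates.

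SAP 5.1.1 lists the same exclusion among the reasons for non-participation, with a different anchor: "Patient enrolled in an investigational drug or device clinical trial in the past 30 days prior to vernakalant administration". SAP 4.2 makes meeting the eligibility criteria a condition of entering the analysis population. Nothing in either document reconciles the two anchors.

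**The concern.** For a prospective patient, enrolment and infusion nearly coincide, so the choice of anchor hardly matters. For a retrospective patient the two dates can be years apart, and the criterion then looks at the weeks before a consent form was signed rather than the weeks before the drug was given.

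Two things are at stake. First, eligibility decides who enters the denominator for HOI incidence, and the written rule sorts retrospective patients on a period unrelated to their treatment. Second, the argument in Protocol 7.2 that both groups meet the same criteria holds in wording only: the window tests the treatment period in one group and a later period in the other.

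**Working it through.** **Inputs.** Planned numbers by country and the Q4 2017 recruitment target: Protocol Appendix I. Target of 2,000 and top planning incidence of 0.22% per HOI: Protocol 10.7. Earliest retrospective treatment, April 2013: Protocol 7.2. Protocol date: 3 August 2016. Enrolment date taken as consent date: SAP 3.4.

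**1. Reproduce Appendix I.**
- Prospective: 110 + 15 + 55 + 60 + 35 + 100 = 375.
- Retrospective: 0 + 0 + 0 + 20 + 70 + 345 = 435.
- Total: 375 + 435 = 810, as stated.
- Retrospective share: 435/2,000 = 21.75% of the target and 435/810 = 53.7% of the patients still to be enrolled.
- Finland supplies 345 of the 435, with enrolment starting in January 2017. Germany supplies none.

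**2. Longest lag from infusion to enrolment**, for a patient treated in April 2013 (range over 30 April to 1 April; days divided by 30.4375):
- to 3 August 2016: 1,191 to 1,220 days, 39 to 40 months;
- to 1 January 2017: 1,342 to 1,371 days, 44 to 45 months;
- to 31 December 2017: 1,706 to 1,735 days, 56 to 57 months.

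These are extremes. The documents do not give the distribution of lags.

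**3. Overlap of the two windows.** With lag L in days, the share of the 30 days before infusion that the written window covers is max(0, 30 − L)/30:
- L = 0: 100%
- L = 7: 23/30 = 77%
- L = 15: 15/30 = 50%
- L ≥ 30: 0%

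Anchored on administration, the share is 100% at every lag.

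**4. What the written rule does at a long lag.** Take two patients infused in 2014 who consent in 2017.
- One joined an investigational trial just before the infusion. The written window lies in 2017, so the patient is eligible. Counted from administration, the patient is excluded.
- The other was in no trial in 2014 but joined an unrelated one two weeks before consenting. The written rule excludes this patient. Counted from administration, the patient is eligible.

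A patient included under a waiver has no consent date, so the written window has no defined end.

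**5. Size.** The documents give no rate of trial participation, so the number misclassified cannot be computed. As an illustration only, assume that 1% to 5% of such patients join a trial in any given 30 days. Then 0.01 × 435 ≈ 4 to 0.05 × 435 ≈ 22 patients could be wrongly kept, and a similar number wrongly excluded. Expected events per HOI among them at 0.22%: 4 × 0.0022 ≈ 0.01 to 22 × 0.0022 ≈ 0.05. At 1.5%, the highest row of Protocol Table 1, 22 patients carry 22 × 0.015 = 0.33. The whole study expects 2,000 × 0.0022 = 4.4 per HOI at the top planning rate.

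**The case against.** The strongest reply is that this is a wording slip with little consequence. Several parts of it stand.

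- **Effect on incidence.** A reader might infer that the HOI estimates are materially distorted, or that a misplaced case is likely. The documents do not support that. Even under the illustrative 5%, 22 of 2,000 patients is 1.1%, and the expected events among them are a small fraction of one. HOI results are also reported separately by method of enrolment, so the prospective estimate is untouched.
- **Two rival eligibility rules.** A reader might infer that protocol and SAP define two different analysis populations. The SAP wording is in a list of reasons for non-participation taken from the site log, for the disposition flow chart and only if available; SAP 4.2 sets no window of its own. What remains is an inconsistency in how one criterion is described. The SAP wording may even show that some logs already counted from administration. Nothing shows which reading sites applied.
- **Purpose of the rule.** Neither document states it. That the rule is meant to keep recent trial participation away from the observed treatment is a reasonable inference, and the SAP wording agrees with it.
- **Limits of re-anchoring.** The criterion concerns joining a trial within 30 days, not exposure. Someone who joined three months before the infusion and was still receiving the trial product would be missed under either anchor.
- **German sites.** The annex has further exclusions and Germany plans no retrospective patients, so its wording matters only for consistency.

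The reply does not remove the defect. Sites that use common sense would be departing from the written criterion, perhaps each in its own way, and a waiver patient cannot be assessed against it at all.

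**Conclusion.** The point holds as a misdirected eligibility rule and an inconsistency between protocol and SAP. For any retrospective patient who consents 30 or more days after treatment, the written window covers none of the pre-infusion period, so it can err in both directions. It has no anchor under a consent waiver. The rule applies to 435 planned patients, about a fifth of the target, and the claim in Protocol 7.2 that both groups meet the same criteria cannot carry the weight placed on it there.

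This rests on two assumptions: that enrolment is dated by consent, as SAP 3.4 does, and that the Appendix I forecast is roughly right. The number of patients misclassified is unknown and the expected effect on HOI incidence is small. Sample size and precision are unaffected. The case for correcting it is that an eligibility rule gating the analysis set should test the right period in every patient.

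**What to change.** In Protocol 6.2 and the synopsis, and in the German annex for consistency, count the 30 days back from the start of the first vernakalant infusion of the index treatment episode instead of from study enrolment. This matches SAP 5.1.1 and gives waiver patients a defined anchor. Apply the same anchor when deciding whether retrospective patients are eligible for the analysis set, wherever the dates of trial participation are available.

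The cost is a protocol amendment and a check of the retrospective records. If the amendment is classed as substantial, Protocol 11.8 and 12.3 require submission to the ethics committees and possibly the authorities before it takes effect. The screening log in Protocol 6.3.2 is specified to hold gender, age and reasons for non-participation, not trial dates, so some records will not settle the question. Reinstating patients already refused is not required: it would need renewed contact and consent or a waiver, for little gain.

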### **6.3 Study Enrolment**

#### **6.3.1 Site Enrolment and Country Selection**

The PASS will target clinical sites in multiple EU member countries to set up infrastructure for prospective data collection on vernakalant IV. Countries currently included are Austria, Denmark, Germany, Spain, and Sweden. Finland, and other EU and non-EU countries may be included but selection is conditional on a number of factors, including, but not limited to, the actual date of product launch in each country and rate of market uptake of vernakalant IV. In addition, country selection was based on the following considerations: (1) the desire for the study to reflect geographic variation of patients across the EU member countries; (2) the ability to capture expected variation in use of different treatment modalities and clinical settings for cardioversion of recent onset AF across EU member countries; and (3) the Sponsor's expectation that in several of these countries, vernakalant IV will be commercially available for use within the first 1-2 months following the expected Commission Decision on the CHMP marketing authorization approval (MAA). The latter consideration was adopted in order to ensure that the study will collect the most timely data on real-world use of vernakalant IV.

Site enrolment progress will be monitored closely following the marketing launch of vernakalant IV across Europe. Any substantial delays in a country with clinical sites will trigger a reevaluation of this country's appropriateness for inclusion in the PASS. Under such circumstances, the Sponsor will inform the CHMP of this development and will consider inclusion of additional countries if needed.

Clinical sites in each country reflecting both academic and community hospitals in which acute cardioversion is routinely performed (IV pharmacologic or electrical) will be targeted for participation in the study. Centres with adequate prescription, hospital encounter, discharge and diagnostic data will be targeted in order to obtain good quality data about administration and expected safety profile of vernakalant IV in the context of normal clinical usage. All efforts will

